### **5.5.2.2 Plasma sampling for drug metabolism analysis**

No additional plasma samples for the quantification of drug metabolites will be collected. For quantification of metabolites backup samples collected for the pharmacokinetic analysis will be used (see [Section 5.5.2.1](#)).

Metabolite analysis will be performed under non-GxP conditions in the laboratory of

Boehringer Ingelheim Pharma GmbH & Co. KG  
Drug Metabolism and Pharmacokinetics  
[name]  
[name]

Proprietary confidential information © 2018 Boehringer Ingelheim International GmbH or one or more of its affiliated companies

Only data related to the parent compound and its metabolites will be acquired. Evaluation of the drug metabolism will be reported separately but not included in the CTR of this trial. The study samples will be discarded after completion of the experiments but not later than 3 years after the final study report has been signed.

#### **5.5.2.3 Urine sampling for pharmacokinetic analysis**

A blank urine sample will be collected before administration of trial medication (within 2 h before drug dosing on days 1) and two 0.5 mL aliquots will be retained to check for analytical interference by concomitant or rescue medication.

All urine voided during the sampling intervals indicated in the [Flow Chart](#) will be collected in 3 L polyethylene (PE) containers and stored at room temperature. Subjects will be told to empty their bladders prior to start of urine sampling interval (this urine will be discarded) and at the end of each sampling interval (this urine will be collected).

The urine weight/volume (weight will be set equal to volume, i.e. 1 kg = 1 L, without correction for specific gravity of urine) for each collection interval will be documented and two 2 mL aliquots (e.g. Nunc tubes) will be stored for bioanalytical measurement. The weight of the empty container including lid will be determined and the weight of the container at the end of each sampling interval will be determined.

Until transfer to the analytical laboratory, the urine samples will be stored at about -20°C or below at the clinical site and stored at the analytical laboratory at -20°C or below until analysis. The back-up aliquots will be transferred to the analytical laboratory after the bioanalyst has acknowledged safe arrival of the first aliquot.

After completion of the trial the urine samples may be used for further methodological investigations, e.g. for stability testing, assessment of metabolites. However, only data related to the analyte and/or its metabolite(s) will be generated by these additional investigations. The study samples will be discarded after completion of the additional investigations but not later than 5 years upon the final study report has been signed.

#### **5.5.3 Analytical determinations**

##### **5.5.3.1 Analytical determination of analyte plasma concentration**

BI 1467335, DI 629956 and CD 6652 concentrations in plasma will be determined by a validated LC-MS/MS (liquid chromatography tandem mass spectrometry) assay.

Proprietary confidential information © 2018 Boehringer Ingelheim International GmbH or one or more of its affiliated companies

The analysis will be performed at:

Boehringer Ingelheim Pharma GmbH & Co. KG  
Drug Metabolism and Pharmacokinetics  
[name]  
[name]

As described in [Section 4.1.5](#), the bioanalyst will be unblinded during sample analysis.

#### **5.5.3.2 Analytical determination of analyte urine concentration**

BI 1467335, DI 629956 and CD 6652 concentrations in urine will be determined by a validated LC-MS/MS assay

The analysis will be performed at:

Boehringer Ingelheim Pharma GmbH & Co. KG  
Drug Metabolism and Pharmacokinetics  
[name]  
[name]

#### **5.6 BIOMARKER(S)**

Not applicable.

## **6. INVESTIGATIONAL PLAN**

### **6.1 VISIT SCHEDULE**

Exact times of measurements outside the permitted time windows will be documented. The acceptable time windows for screening and end of trial examination are given in the [Flow Chart](#).

Study measurements and assessments scheduled to occur ‘before’ trial medication administration on Day 1 are to be performed and completed within a 2 h-period prior to the trial drug administration (only on Day 1 this includes blank values for PK in urine and plasma).

On Day 14 and 28, same time windows apply except of the plasma PK sample which will be collected 5 minutes before drug administration.

The acceptable deviation from the scheduled time for vital signs and ECG will be  $\pm$  30 min for the first 4 h after trial drug administration and  $\pm$  60 min thereafter when not already stated otherwise in the [Flow Chart](#).

If scheduled in the [Flow Chart](#) at the same time as a meal, 12-lead ECG recordings followed by vital signs have to be done first. Furthermore, if several measurements including venipuncture are scheduled for the same time, venipuncture should be the last of the measurements prior to meal due to its inconvenience to the subject and possible influence on physiological parameters.

For planned individual plasma concentration sampling times and urine collection intervals refer to the [Flow Chart](#). While these nominal times should be adhered to as closely as possible, the actual sampling times will be recorded and used for determination of pharmacokinetic parameter.

If a subject misses an appointment, it will be rescheduled if possible. The relevance of measurements outside the permitted time windows will be assessed no later than at the Blinded Report Planning Meeting.

### **6.2 DETAILS OF TRIAL PROCEDURES AT SELECTED VISITS**

#### **6.2.1 Screening period**

After having been informed about the trial, all subjects will give their written informed consent in accordance with GCP and local legislation prior to enrolment in the study.

For information regarding laboratory tests (including drug and virus screening), ECG, vital signs, and physical examination, refer to [Sections 5.2.3 to 5.2.5](#).

Pharmacogenomic genotyping will be performed in all volunteers (for details see [Section 5.3](#)).

#### **6.2.2 Treatment period**

Each subject will receive a single dose of BI 1467335 from Day 1 to Day 28.

Proprietary confidential information © 2018 Boehringer Ingelheim International GmbH or one or more of its affiliated companies

Study participants will be admitted to the trial site in the evening of day -1 and kept under close medical surveillance for at least 24 h following the first drug administration. The subjects will be kept hospitalized from the evening of Day -1 to the morning of Day 2, the evening of Day 13 to the morning Day 15 and from the evening of Day 27 to the morning of Day 29. On all other time periods the study will be performed in an ambulatory fashion provided there are no medical reasons preventing the discharge from the unit.

The safety measurements performed during the treatment period are specified in [Section 5.2](#) of this protocol and in the [Flow Chart](#). For details on time points for all other trial procedures, refer to the [Flow Chart](#). AEs and concomitant therapy will be assessed continuously from screening until the end of trial examination. For details on time points and procedures for collection of plasma and urine samples for PK analysis, refer to [Flow Chart](#) and [Section 5.5.2](#).

### **6.2.3      End of trial period**

For AE assessment, laboratory tests, PK sampling, recording of ECG and vital signs, and physical examination during the end of trial period, see [Sections 5.2.2](#) to [5.2.5](#).

Subjects who discontinue treatment before the end of the planned treatment period should undergo the end of trial visit.

All abnormal values (including laboratory parameters) that are judged clinically relevant by the investigator will be monitored using the appropriate tests until a return to a medically acceptable level is achieved. (S)AEs persisting after subject's end of trial must be followed up until they have resolved, have been sufficiently characterised, or no further information can be obtained.

The end of the trial as a whole is defined by the 'last regular visit completed by last subject' or 'end date of the last open AE' or 'date of the last follow-up test' or 'date of an AE has been decided as sufficiently followed-up', whichever is latest.

## 7. STATISTICAL METHODS AND DETERMINATION OF SAMPLE SIZE

### 7.1 STATISTICAL DESIGN – MODEL

#### 7.1.1 Objectives

The primary objective of this trial is to investigate the effect of moderate renal impairment (test, T) on the pharmacokinetics and safety of BI 1467335 in comparison to a control group with normal renal function (reference, R) after single 10 mg BI 1467335 treatment for 28 days. The trial is designed to allow intra-subject comparisons (via pairs of renal impaired subjects and their matching healthy controls) and will be evaluated statistically by use of an appropriate linear model which is further described in [Section 7.1.3](#).

The secondary objective is the evaluation and comparison of several pharmacokinetic parameters between subject groups (moderate renal impaired and normal renal function). The secondary objectives will be assessed by descriptive statistics.

The assessment of safety and tolerability will be an additional objective of this trial, and will be evaluated by descriptive statistics.

#### 7.1.2 Endpoints

The effect of moderate renal impairment is to be determined on the basis of the primary endpoints  $C_{max}$ ,  $AUC_{0-24}$  of BI 1467335 on Day 1, and  $C_{max,28}$  and  $AUC_{\tau,28}$  of BI 1467335 on Day 28 (see [Section 5.5.1](#)) as well as the secondary pharmacokinetic endpoints  $C_{max,14}$  and  $AUC_{\tau,14}$  of BI 1467335 on Day 14 (see [Section 5.5.2](#))

Safety and tolerability will be determined on the basis of the parameters specified in [Section 5.2.1](#).

#### 7.1.3 Model

The statistical model used for the analysis will be an ANOVA (analysis of variance) model on the logarithmic scale including the effect "degree of renal impairment" as a fixed effect as well as subject pair as a random effect. The model is described by the following equation:

$$y_{ik} = \mu + \tau_k + s_i + \varepsilon_{ik}, \text{ where}$$

$y_{ik}$  logarithm of response (endpoint for relative bioavailability evaluation, (see in [Section 7.1.3](#)) measured on the degree of renal impairment k for subject pair i,

$\mu$  the overall mean,

$s_i$  the ith subject pair (each renal impaired subject has his own matching healthy control),  $i=1, \dots, 10$

$\tau_k$  the kth degree of renal impairment, k = 1 for normal and k=2 for moderate renal impaired

$\varepsilon_{ik}$ , the random error associated with the kth degree of renal impairment for subject pair i.

## **7.2 NULL AND ALTERNATIVE HYPOTHESES**

The effect of renal impairment on the pharmacokinetics of BI 1467335 will be evaluated via comparing moderate renal impaired subjects to their matched subjects with normal renal function. This will be estimated by the ratios of the geometric means (test/reference) for the PK endpoints mentioned in [Section 7.1.2](#). Additionally, their two-sided 90% confidence intervals (CIs) will be provided. This method corresponds to the two one-sided t-tests procedure, each at the 5% significance level. Since the main focus is on estimation and not testing, an acceptance range was not specified, that is, no hypothesis will be tested.

## **7.3 PLANNED ANALYSES**

Adherence to the protocol (such as inclusion/exclusion criteria, times of measurement, compliance with intake of trial medication, treatment dispensing errors, prohibited concomitant medication, completeness and consistency of data) will be checked. Important protocol violations will be identified no later than in the Report Planning Meeting and provided in the Trial Statistical Analysis Plan (TSAP).

The following analysis sets will be defined for this trial:

Further analysis sets will be defined in the TSAP, if needed.

- Randomised set (RS):

This subject set includes all subjects who were randomized, i.e., who have been assigned a study subject number, whether treated or not.

- Treated set (TS):

This subject set includes all subjects in the RS who were documented to have received one dose of study drug. This is the full analysis set population in the sense of ICH-E9.

- PK analysis set (PKS):

Plasma and urine concentration data and parameters of a subject will be included in the statistical pharmacokinetic (PK) analyses if they are not flagged for exclusion due to a protocol violation relevant to the evaluation of PK (to be decided no later than in the Report Planning Meeting) or due to PK non-evaluability (as revealed during data analysis, based on the criteria specified below). Exclusion of a subject's data will be documented in the CTR.

Proprietary confidential information © 2018 Boehringer Ingelheim International GmbH or one or more of its affiliated companies

Relevant protocol violations may be

- Incorrect dose of trial medication taken
- Use of restricted medications.

Plasma and urine concentrations and/or parameters will be considered as non-evaluable, if for example

- the subject experienced emesis that occurred at or before two times median  $t_{max}$  of the respective treatment (Median  $t_{max}$  is to be determined excluding the subjects experiencing emesis),
- missing samples/concentration data at important phases of PK disposition curve.

The PK analysis set (PKS) includes all subjects in the TS who provide at least one PK parameter that was defined as primary or secondary endpoint and was not excluded according to the description above. Thus, a subject will be included in the PKS, even if he/she contributes only one PK parameter value to the statistical assessment.

- PK statistical analysis set (PKS-stat):

This subject set includes all subjects from the PKS who built a subject pair of renal impaired subject and his matching healthy volunteer control and provide at least one PK parameter that was defined as primary or secondary endpoint and was not excluded according to the description above.

### 7.3.1 Primary analyses

The primary analyses of the primary endpoint will be based on the PKS-stat (cf. [Section 7.3](#)).

Point estimates of the ratios of the geometric means (T/R) for the endpoints described in [Section 7.1.2](#) and their two-sided 90% confidence intervals (CIs) will be provided.

To this end, the PK endpoints will be log-transformed (natural logarithm) prior to fitting the ANOVA model (cf. [Section 7.1.3](#)). For each endpoint, the difference between the expected means for  $\log(T)-\log(R)$  will be estimated by the difference in the corresponding adjusted means (Least Squares Means), and a two-sided 90% confidence interval based on the t-distribution will be computed. These quantities will then be back-transformed to the original scale to provide the point estimate and 90% CIs for each endpoint.

### 7.3.2 Secondary analyses

Pharmacokinetic endpoints defined in [Section 5.5.1](#) will be compared between subject groups (moderate renal impaired and normal renal function) by means of descriptive evaluations, as described in [Section 7.3.5](#) based on the PKS. In addition, the same pharmacokinetic parameters that will be evaluated with inferential statistics for BI 1467335, will be evaluated

Proprietary confidential information © 2018 Boehringer Ingelheim International GmbH or one or more of its affiliated companies

in the same manner for the 2 major metabolites, DI 629956 and CD 6652 and the ratios of parent to CD6652 and parent to DI 629956.

Additionally the relationship of estimated renal function and the primary and secondary PK endpoints will be investigated using a regression model, if the data allows. In case of too narrow renal function range only a scatterplot will be provided.

Safety and tolerability will be evaluated by descriptive evaluations, as described in [Section 7.3.3](#).

### **7.3.3 Safety analyses**

Safety will be assessed for the further parameters of interest listed in [Section 5.2.1](#). All treated subjects (that is, all subjects who received at least one dose of study drug), will be included in the safety analysis (TS). Safety analyses will be descriptive in nature and will be based on BI standards. No hypothesis testing is planned.

The analyses will be done by 'treatment at onset'.

Treatments will be compared in a descriptive way. Tabulations of frequencies/proportions will be used for the evaluation of categorical (qualitative) data, and tabulations of descriptive statistics will be used to analyse continuous (quantitative) data.

Measurements (such as ECG, vital signs, or laboratory parameters) or AEs will be assigned to treatments (see [Section 4.1](#)) based on the actual treatment at the planned time of the measurement or on the recorded time of AE onset (concept of treatment emergent AEs).

Therefore, measurements planned or AEs recorded prior to first intake of trial medication will be assigned to 'screening' and those between first trial medication intake until the trial completion date will be assigned to the treatment period. These assignments including the corresponding time intervals will be defined in detail in the TSAP.

Additionally, further treatment intervals (analysing treatments) may be defined in order to provide summary statistics for time intervals, such as combined treatments, on-treatment totals or periods without treatment effects (such as screening and post-study intervals).

Adverse events will be coded using the Medical Dictionary for Regulatory Activities (MedDRA). Frequency, severity and causal relationship of AEs will be tabulated by treatment, system organ class and preferred term. SAEs, AESIs (see [Section 5.2.2.1](#)) and other significant AEs (according to ICH E3) will be listed separately.

Laboratory data will be compared to their reference ranges. Values outside the reference range as well as values defined as clinically relevant will be highlighted in the listings. Additionally, differences from baseline will be evaluated.

Vital signs or other safety-relevant data observed at screening, baseline, during the course of the trial and at the end-of-trial evaluation will be assessed with regard to possible changes compared to findings before start of treatment.

Relevant ECG findings will be reported as AEs.

### **7.3.4      Interim analyses**

No interim analysis is planned. However, as mentioned in [Section 2.3](#) a staggered inclusion of renally impaired subjects will be applied, where based on the safety and PK data of the first 3 subjects up to one week after start of dosing, it will be decided whether the remaining subjects can be dosed. For this purpose exploratory evaluation of safety and PK data will be performed.

### **7.3.5      Pharmacokinetic analyses**

The pharmacokinetic parameters listed in [Section 5.5.1](#) for drug BI 1467335 will be calculated according to the BI SOP 'Standards and processes for analyses performed within Clinical Pharmacokinetics/Pharmacodynamics' [[001-MCS-36-472](#)].

Subjects who are not included in the PKS (refer to [Section 7.3.1](#)) will be reported with their individual plasma / urine concentrations and individual pharmacokinetic parameters; however, they will not be included in descriptive statistics for, pharmacokinetic parameters or other statistical assessment.

Only concentration values within the validated concentration range and actual sampling times will be used for the calculation of pharmacokinetic parameters. Concentrations used in the pharmacokinetic calculations will be in the same format provided in the bioanalytical report, (that is, to the same number of decimal places provided in the bioanalytical report).

Descriptive evaluations of PK parameters listed in 5.5.1 are based on PKS.

The following descriptive statistics will be calculated for analyte concentrations as well as for all pharmacokinetic parameters: N, geometric mean, geometric coefficient of variation, arithmetic mean, arithmetic coefficient of variation, standard deviation, minimum, median, and maximum. The data format for descriptive statistics of concentrations will be identical with the data format of the respective concentrations. The descriptive statistics of pharmacokinetic parameters will be calculated using the individual values with the number of decimal places as provided by the evaluation program. Then the individual values as well as the descriptive statistics will be reported with three significant digits in the clinical trial report.

## **7.4          HANDLING OF MISSING DATA**

### **7.4.1       Safety**

With respect to safety evaluations, it is not planned to impute missing values.

### **7.4.2       Plasma/urine drug concentration - time profiles**

Handling of missing PK data will be performed according to the relevant SOP of the Sponsor [[001-MCS-36-472](#)].

For tabulation and graphical displays, drug concentration data identified with NOS (no sample available), NOR (no valid result), NOA (not analysed), or BLQ (below the lower

limit of quantification) will be displayed as such and not replaced by zero at any time point (this rule also applies also to the lag phase, including the pre-dose values).

#### **7.4.3 Pharmacokinetic parameters**

No imputation of missing PK parameters will be performed

For the calculation of PK parameters by non-compartmental analysis, concentration data identified with NOS, NOR or NOA will generally not be considered. Concentration values in the lag phase identified as BLQ will be set to zero. All other BLQ values of the profile will be ignored. The lag phase is defined as the period between as the period between time zero and the first time point with a concentration above the quantification limit.

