#### *Pharmacokinetics in healthy subjects*

Following both single and multiple doses of 10 and 15 mg, BI 1467335 Cmax and AUC0-24 increased in a more than dose proportional manner on Days 1, 14 and 28 ([Figure 1.2: 1](#)). Resulting from the accumulation of BI 1467335 following repeat oral dosing, quantifiable BI

Proprietary confidential information © 2018 Boehringer Ingelheim International GmbH or one or more of its affiliated companies

1467335 concentrations could be measured up to 4 h and 8 h postdose for 10 and 15 mg respectively on Day 1; and up to 24 h postdose on Days 14, and Day 28. Resulting from the limited time period over which quantifiable BI 1467335 concentrations could be measured on Day 1; the resulting  $AUC_{0-24}$  values on Day 1 need to be regarded with caution, as they may be underestimates, due to the large number of concentrations below the assays lower limit of quantification

The observed apparent elimination half-life (gMean) for BI 1467335 is significantly shorter on Day 1 (<1 h) compared to Days 14 and 28, (<4 h following 10 mg and < 9 h following 15 mg on Day 28). Despite the short apparent elimination half-lives, BI 1467335 significantly accumulates following q.d. dosing. For 10 mg q.d.,  $C_{max}$  increased by approximately 26-fold on Day 14 and 40-fold on Day 28, and  $AUC_{0-24}$  increased by approximately 58-fold on Day 14 and 159-fold on Day 28. For 15 mg q.d. dosing,  $C_{max}$  increased by approximately 14-fold on Day 14 and 16-fold on Day 28, and  $AUC_{0-24}$  increased by approximately 72-fold on Day 14 and 82-fold on Day 28.

Taking all the BI 1467335 data together, including trough concentrations, 1 h postdose samples along with  $AUC_{0-24}$  values, they suggest that steady state may be attained close to Day 14 following 15 mg q.d., whereas it was not attained by Day 14 following 10 mg q.d.. Following 10 mg q.d.,  $C_{max}$  and  $AUC_{0-24}$  are approximately 54% and 180% higher respectively on Day 28 compared to that on Day 14, whereas following 15 mg q.d.,  $C_{max}$  and  $AUC_{0-24}$  are approximately 13 and 15 % higher respectively on Day 28 compared to that on Day 14. For further details, please refer to the current 'Investigator's Brochure (IB)' [\[c04751792\]](#).

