## **2. RATIONALE, OBJECTIVES, AND BENEFIT - RISK ASSESSMENT**

### **2.1 RATIONALE FOR PERFORMING THE TRIAL**

An association between NAFLD/NASH and impaired renal function was consistently shown in numerous epidemiological studies [[P16-05590](#)] and may be due to common underlying inflammatory pathways in liver and kidney. BI 1467335 is going to enter phase IIb in a NASH population. Taking the published epidemiological data into consideration this may be associated in up to 20% of NASH patients with a reduced GFR < 60 ml/min i.e. at least moderate renal impairment.

Based on both the preclinical and ongoing clinical phase I study 1386.8, renal clearance is considered to be involved in the elimination of BI 1467335, especially following multiple dosing. The study is conducted to support the safe inclusion of NASH patients who may have moderate renal impairment in Phase IIb/III studies.

The PK will be investigated during a 4 week treatment with 10 mg of BI 1467335 q.d. which has already been shown to be well tolerated in healthy subjects. A dose of 10 mg is the planned maximum therapeutic dose in a NASH population. Currently 20 mg q.d. is being investigated in HVs. Preliminary 15 mg q.d. in HVs on Day 28 resulted in gMean  $C_{max}$  and  $AUC_{0-24}$  values approximately 2.6 and 4.7-fold higher than those observed on Day 28 following 10 mg q.d..

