#### **4.1.5 Blinding and procedures for unblinding**

This Phase I trial will be handled in an open fashion throughout (i.e. during the conduct, including data cleaning and preparation of the analysis). This is considered acceptable because the potential for bias seems to be low and does not outweigh practical considerations.

Emergency envelopes will not be provided, since all subjects receive the same dose and study is an open label design.

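### Must the plan itself state how Day-1 AUC0-24 is completed after the last quantifiable sample?

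*Protocol*

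**What the plan says.** Protocol Section 5.5.1.1 and SAP Section 5.1 make AUC0-24 after the first dose a primary endpoint over a fixed 24-hour interval. Section 5.5.1.3 lists AUC0-tz, the area to the last quantifiable sample, as a separate further parameter, along with the extrapolated percentage of AUC and the half-life.

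Section 7.4.3 gives the calculation rules. Values coded as no sample, no valid result or not analysed are generally left out. BLQ values in the lag phase become zero. For the rest, "All other BLQ values of the profile will be ignored". It also says "No imputation of missing PK parameters will be performed".

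The background in Section 1.2 reports for the earlier study that "concentrations could be measured up to 4 h and 8 h postdose for 10 and 15 mg respectively on Day 1". It asks for caution with those Day-1 AUC0-24 values, "as they may be underestimates, due to the large number of concentrations below the assays lower limit of quantification".

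For the calculation itself, Protocol Sections 7.3.5 and 7.4.2 point to the sponsor's SOP 001-MCS-36-472. SAP Section 6.6 and the SAP Section 7 paragraph on excluding concentrations point to its noncompartmental reference document.

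**The concern.** The protocol foresees the difficulty in its background but does not visibly resolve it in its analysis sections. The Day-1 flow chart has 13 post-dose plasma samples, and five of them (6, 8, 10, 12 and 23:55 h) fall after 4 h. If those five are BLQ and are ignored, three readings seem possible: stop at the last quantifiable sample, extrapolate to 24 h with the terminal slope, or call the parameter non-evaluable.

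Non-evaluability is defined only by examples (Protocol Section 7.3, SAP Section 6.3) and may emerge during data analysis. The trial is open throughout, "including data cleaning and preparation of the analysis", so renal group would be known when the choice is made. If renal impairment prolongs the quantifiable period, the completion rule could act unequally on the two groups and shift a primary ratio. If profiles were excluded, pairs would drop out of a set of only ten.

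**Working it through.** There is no figure in the plan to reproduce: the sample size rests on no power calculation. The check is a reading of the text followed by an illustration of size.

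**What the text already narrows**

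- AUC0-tz is listed separately, so AUC0-24 is not meant to be the same quantity.
- Zero is used for BLQ only in the lag phase. Filling the tail with zeros, or drawing a line to zero at 24 h, conflicts with ignoring later BLQ values.
- Section 7.4.3 treats BLQ apart from the codes for absent results. The non-evaluability example concerns missing samples or data, so a BLQ tail is not naturally "missing". The ban on imputation concerns missing parameters, not BLQ concentrations.

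**Size per subject**

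From the documents: the Day-1 sampling times, a last quantifiable time of 4 h and a half-life below 1 h. Assumed: one-compartment oral profile, ka = 4 per h, linear trapezoids, terminal slope known.

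With k = ln 2 / half-life, C(t) = ka/(ka − k) × (e^(−kt) − e^(−ka·t)). Let A be the area to the last quantifiable time tl, and L the concentration there.

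- Stop at last sample: A
- Zero at next sample (for comparison only): A + L(t_next − tl)/2
- Terminal-slope extrapolation: A + (L/k)(1 − e^(−k(24 − tl)))

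For a 1 h half-life, A = 1.327, L = 0.0756 and k = 0.693. Zero at next sample gives 1.327 + 0.0756 = 1.403, or 1.057 × A. Extrapolation gives 1.327 + 0.109 = 1.436, or 1.082 × A.

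| Half-life (h) | Zero at next / stop | Extrapolation / stop |
|---|---|---|
| 0.5 | 1.008 | 1.006 |
| 0.75 | 1.031 | 1.033 |
| 0.9 | 1.047 | 1.061 |
| 1.0 | 1.057 | 1.082 |

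**Size in the impaired/normal ratio** (each group shown as half-life / last quantifiable time)

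| Normal | Impaired | Stop | Zero at next | Extrapolation |
|---|---|---|---|---|
| 0.9 h / 4 h | 0.9 h / 4 h | 1.00 | 1.00 | 1.00 |
| 1 h / 4 h | 1.5 h / 6 h | 1.52 | 1.49 | 1.51 |
| 1 h / 4 h | 2 h / 8 h | 2.03 | 1.97 | 2.02 |
| 1 h / 2 h | 1.5 h / 4 h | 1.79 | 1.71 | 1.51 |

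In the second and third rows the spread is at most 2.03/1.97 = 1.03. The last row, with quantification in normal subjects ending at 2 h, is the unfavourable case: 1.79/1.51 = 1.19.

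A wider simulation varied absorption (ka 3 or 6 per h), a possible slow phase, subject CV (30% or 50%) and the quantification limit over 276 settings. With equal exposure, bias stayed within 2%. With the whole profile doubled, median bias was +3.0% for stopping (range +0.5 to +7.6%) and +0.7% for extrapolation (−0.1 to +4.4%). With half-life going from 0.8 to 1.6 h, the medians were +4.8% and +3.5%; from 0.8 to 1.0 h, +1.4% and +1.6%.

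**Against sampling error**

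The 90% CI factor for 10 pairs is exp(t(0.95, 9) × √(2/10) × √ln(1 + CV²)), ignoring within-pair correlation.

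- CV 30%: exp(1.833 × 0.447 × 0.294) = 1.27
- CV 50%: exp(1.833 × 0.447 × 0.472) = 1.47

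**The case for a change.** The best case for a change is that this is a primary endpoint, the protocol itself names the problem, Section 7.4.3 already writes out part of the BLQ rule, and one sentence would finish it before anyone looks at data with renal group known. Excluding profiles would also cost precision: at an assumed CV of 50%, going from 10 to 6 pairs widens the CI factor from 1.47 to 1.73.

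Some of this stands. The visible text does not spell out the completion rule, and a reader without the sponsor's standard cannot reproduce the number.

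The rest is weaker. One cannot claim that the plan lacks the rule. It refers to a standard that is not available here. SAP Section 7.6 is absent from the released text, and SAP reference 8, the PK analysis standard, is cited nowhere in what remains. The loss of pairs presupposes an exclusion rule for BLQ tails that neither document contains. Nor is there a clearly better rule to ask for: extrapolation has the smaller median bias when the whole profile is scaled, but not for a half-life change from 0.8 to 1.0 h. Open handling is tempered by the requirement in Protocol Section 7.3 and SAP Section 6.3 to document exclusions in the trial report.

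**Conclusion.** No change is needed. This is a detail that the sponsor's PK standard may well settle and that a pharmacokineticist would fill in sensibly, in the same way for both groups. The expected effect is a few percent on one of four primary ratios, against confidence limits a factor of about 1.27 to 1.47 either side of the estimate. No hypothesis is tested. Day-1 Cmax and the Day-14 and Day-28 endpoints are not materially affected. The planned half-life and extrapolated percentage, where the data allow them, would show a reader how much of the Day-1 area was observed.

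This rests on assumed profiles and CVs, a Day-1 half-life below 1 h, and quantification to about 4 h. That last figure comes from preliminary healthy-subject data with an oral solution, whereas this trial uses tablets, and no quantification limit is given. If normal subjects fell below the limit by about 2 h while impaired subjects did not, the rules could differ by about 19% in the ratio. That is still less than the 27% upper margin at a CV of 30%, but worth a remark when the result is interpreted.
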